3.4.1.4 Discontinuation

If an eligible Subject drops out of the study for any reason, the Investigator must make every reasonable effort to obtain clinical assessments of adverse events. All data should be recorded in the CRF for the Subject and the reason for the drop out should be documented.

In the event that a Subject drops out of the study due to an adverse event, the nature of the event and its clinical course must be fully documented. The Investigator must attempt to follow the Subject until the adverse event has resolved, become clinically insignificant, stabilized, or the Subject is lost to follow-up.

Subjects who drop out of the study without completing the three 45-minute treatments over the course of the first week (within 7 calendar days) will be considered premature drop out. The Sponsor will take reasonable action to replace any of the Subjects who drop out prematurely to maintain the 5-Subject enrollment.

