2.0 STUDY OBJECTIVES

The purpose of this study is to assess the clinical feasibility of DeviceFarm, Inc.'s RenewalNail™ system and the treatment protocol that was developed based on extensive laboratory testing on human cadaver nails.

The primary objective of this study is to evaluate the efficacy and safety of the RenewalNail™ plasma treatment system and Protocol in achieving mycological cure for the patient. The Protocol calls for three 45-minute treatments performed over a week to achieve mycological cure. Mycological cure will be assessed with two consecutive mycological culture tests done over a week. Two consecutive negative mycology culture results confirm the elimination of fungus causing onychomycosis infection, as recommended by recent FDA guidance. There will be no placebo arm in the study.

Secondary objectives include:

- Will the treatment protocol result in clear nail growth for the patient over a 5-month interval?
- Is the instrument functional in a clinical setting as related to user instructions, user interface and human factor analysis?
- Are there treatment protocol or instrument changes that would improve the treatment results, patient safety, or patient comfort?
- Are there fungal species beyond *Trichophyton rubrum* and *Trichophyton mentagrophytes* that are not affected by the treatment, as seen in species identification from the nail scrapings?

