3.0 INVESTIGATIONAL PLAN

3.1 Overall Study Design

DeviceFarm, Inc.'s Early Feasibility Study will be conducted as a Single-center open-label study in Subjects who meet the specified inclusion/exclusion criteria. Informed consent will be obtained. Characteristics of patients including age, gender, disease severity, and disease history will be documented during the screening visit.

Five Subjects with Distal Subungual Onychomycosis (mild to moderate DSO) infection of their big toe (hallux) nail infected by the dermatophytes *Trichophyton (T.) rubrum* or *T. mentagrophytes* will be enrolled.

Treatments will be performed at the office of the Investigator as elaborated in the **3.4 Conduct of Study** section below. The treatment protocol outlines three 45-minute treatments over the course of the first week (within 7 calendar days).

Primary study endpoint will be mycological cure, which is defined as two consecutive negative cultures following treatment. Mycological cultures will be collected (1) during screening, (2) after the third treatment, and (3) around a week (5-15 calendar days) after the third treatment.

CONFIDENTIAL

Secondary study endpoint will be clear nail growth. Photographs of the target toes will be taken throughout the study to track clear nail growth.

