3.2 Discussion of Study Design

This study will be conducted as a Single-center, open-label, pilot study involving 5 Subjects. After giving informed consent, each Subject will be screened for eligibility according to inclusion/exclusion criteria. A Subject will be considered evaluable if he or she satisfies all admission criteria for entry into the study and completes the treatment protocol.

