3.3.3 Withdrawal Criteria

Withdrawal criteria include but are not limited to the following:

CONFIDENTIAL

- Investigator's request;
- Safety reasons (e.g., severe adverse reactions);
- Subject's request;
- Poor compliance;
- Subjects lost to follow-up. The Investigator will try to reach the Subject, twice by telephone and once by certified letter, before considering the Subject lost-to-follow-up. These actions will be reported on the Final Case Report Form and a copy of the follow-up letter will be maintained in the Investigator's file.

Treatment may be discontinued at any time by the investigator if, in his/her clinical judgment, it is in the best interest of the Subject, treatment is deemed inappropriate by a physician evaluation, or if the Subject cannot comply with the protocol. All premature discontinuations and their causes must and will be carefully documented by the Investigator on the Final Case Report Form and, if need be, on the Adverse Event Case Report Form.

Subjects who did not complete the entire study should be fully evaluated when possible. The procedures designated for the Final Visit should be completed for all Subjects discontinuing. Subjects are free to withdraw from participating in this study at any time and for whatever reason, specified or unspecified, and without prejudice.

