9.0 Statistical Methods Planned

Due to the nature of the study and the small number of Subjects, no inferential statistical analyses will be performed. The results from this study will be used to determine whether the treatment can achieve mycological cure for onychomycosis Subjects fulfilling the inclusion/exclusion criteria.

Mycological cure is defined as an achievement of negative culture results for both *Trichophyton rubrum* and *Trichophyton mentagrophytes* from both Visit 3 and Visit 4.

The data is too small to summarize with descriptive statistics; therefore, Subject listings will be presented.

CONFIDENTIAL

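### Evaluability requires completing all three sessions and early drop-outs are replaced, so any cures-out-of-five reading of the primary endpoint covers completers only

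*Protocol*

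**What the plan says.** - **Who is evaluable (Protocol 3.2):** "A Subject will be considered evaluable if he or she satisfies all admission criteria for entry into the study and completes the treatment protocol". Section 3.1 describes that treatment protocol as three 45-minute sessions within 7 calendar days.
- **Who is replaced (3.4.1.4):** the premature drop-outs are "Subjects who drop out of the study without completing the three 45-minute treatments over the course of the first week", and "The Sponsor will take reasonable action to replace any of the Subjects who drop out prematurely to maintain the 5-Subject enrollment". The rule applies whatever the reason for leaving and sets no limit on the number replaced.
- **Primary endpoint (3.1):** "Primary study endpoint will be mycological cure, which is defined as two consecutive negative cultures following treatment". Section 9.0 requires the negative results to come "from both Visit 3 and Visit 4", and section 4.2 places them after the treatment week is complete.
- **Reporting (9.0):** no inference and no descriptive summaries of efficacy, only listings by subject. The stated use of the results is to judge whether the treatment can achieve cure in patients who meet the entry criteria.
- **Drop-outs (3.3.3 and 3.4.1.4):** data and reasons for leaving are recorded, and the Final Visit procedures are to be done for those who discontinue.

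**The concern.** Completing the course happens after enrolment, and the treatment itself can prevent it. Section 3.3.3 lists safety among the withdrawal reasons, section 3.4.2.2 foresees stopping for a serious adverse event, and section 5.0 names heat, discomfort and blistering as possible effects. A subject who leaves after one or two sessions for such a reason, or because the device could not deliver the remaining sessions, is not evaluable under 3.2 and is replaced under 3.4.1.4.

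In a feasibility study of this regimen, that event is part of the answer. Section 2.0 puts the system and its treatment protocol together in the primary objective, and asks as a secondary question: "Are there treatment protocol or instrument changes that would improve the treatment results, patient safety, or patient comfort". Section 9.0 addresses patients who meet the entry criteria, whereas the only population the protocol defines consists of those who also finished. At stake is how a result out of five will be understood when the next study is planned.

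**Working it through.** **Inputs.** Planned number: 5 (section 3.3). Evaluability and replacement rules: 3.2 and 3.4.1.4. Endpoint cultures: Visits 3 and 4 (9.0). The protocol gives no stopping rate, cure rate, alpha or power, so it has no figure to reproduce.

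**Step 1: what is known about an early stopper.** A subject who leaves before Visit 3 has neither endpoint culture. The procedures required at discontinuation are those of Visit 6 (3.4.2.7), which include no culture. Under the definitions in 4.2 and 9.0 such a subject cannot meet the definition of cure. The true mycological state is unknown.

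**Step 2: direction and size.** Let x be the cures among five completers and k the treated subjects who were replaced, classed as not achieving cure. The completer fraction is x/5 and the all-treated fraction is x/(5+k). The difference is x/5 − x/(5+k) = xk/[5(5+k)], which is never negative.

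| Cures among 5 completers | k = 0 | k = 1 | k = 2 |
|---|---|---|---|
| 5 | 5/5 = 100% | 5/6 = 83.3% | 5/7 = 71.4% |
| 4 | 4/5 = 80% | 4/6 = 66.7% | 4/7 = 57.1% |
| 3 | 3/5 = 60% | 3/6 = 50.0% | 3/7 = 42.9% |

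For example, x = 5 and k = 1 gives 5/30 = 16.7 points; x = 3 and k = 2 gives 6/35 = 17.1 points. For scale, the exact (Clopper-Pearson) 95% interval is 47.8–100% for 5/5 and 35.9–99.6% for 5/6, so the shift is small beside the sampling uncertainty. It differs in kind, because it always runs the same way.

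**Step 3: how often a replacement might occur.** The stopping probability d is an assumption. The chance that at least one of the first five is replaced is 1 − (1 − d)^5, and the expected number treated to obtain five completers is 5/(1 − d).

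| Assumed d | At least one replaced | Expected number treated |
|---|---|---|
| 5% | 22.6% | 5.26 |
| 10% | 41.0% | 5.56 |
| 20% | 67.2% | 6.25 |
| 30% | 83.2% | 7.14 |

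**Step 4: do the two rules match?** A subject who receives the third session after day 7 but stays in the study has, read literally, not completed the 7-day course (not evaluable under 3.2). That subject has not dropped out either (not replaced under 3.4.1.4). Conversely, a subject lost between Visits 3 and 4 is evaluable and not replaced, yet lacks the second culture. The protocol does not say how either is classified for the primary endpoint.

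**The case against.** The best defence is that nothing in section 9.0 computes a cure rate. It plans listings, does not use the term evaluable, and does not confine the listings to completers. Reasons for leaving are documented, so a careful reader of full listings could see each early stopper. The question is proof of concept, for which completer data are relevant, and analysis sets are often left to a statistical analysis plan, which may exist but is not at hand.

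Much of this stands, and it rules out several stronger readings that a reader might infer:

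- *That the plan reports a biased cure percentage.* It does not; no proportion or denominator is written.
- *That device failures in general disappear.* Only failures that prevent completion are affected. A subject who completes the course and stays culture-positive remains an evaluable failure.
- *That safety or tolerability data are lost.* Sections 3.4.1.4, 5.1 and 9.1 collect and report adverse events without an evaluability filter.
- *That each replaced subject is a known non-cure.* The endpoint cultures are missing, so the accurate label is cure not demonstrated.

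The rest does not answer the point. The protocol itself fixes evaluability and replacement, so these are not matters merely left for later. Recording a reason on a case report form does not say whether a replaced subject appears in the efficacy listing, or how that subject is classified.

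**Conclusion.** The point holds in a limited form. The protocol defines one population, completers, replaces those who leave early for any reason, and defines no all-treated efficacy set. A count of cures out of five would therefore describe completers only, and the selection could make it look better but never worse.

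The size depends on the number replaced: with one, 5/5 against 5/6; with two, 3/5 against 3/7. These figures assume that early stoppers are classed as not achieving cure. If nobody stops early, there is no effect. The probabilities of replacement rest entirely on assumed stopping rates. No type I error or power is involved, because no test is planned. The point concerns how the primary result is presented and read, and it is worth settling before results are known because the change is only to wording.

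**What to change.** - **Sections 3.2 and 9.0:** make the primary efficacy listing every enrolled subject who started at least one plasma session. Classify anyone who did not complete the three sessions, or who lacks either the Visit 3 or the Visit 4 culture, as not having demonstrated mycological cure. Apply this whatever the recorded reason, including subject request, poor compliance and loss to follow-up; otherwise a withdrawal for discomfort recorded as the subject's own request would escape the rule. Show the reason and the number of sessions received.
- **Supporting listing:** keep the completers, under the existing evaluable label.
- **Section 3.4.1.4:** keep replacement, but state that replaced subjects who received any treatment stay in the efficacy listings, and that the numbers treated, replaced and completed are reported together.
- **Timing:** keep subjects who finished the three sessions outside the 7-day limit in the primary listing, flagged as deviations.

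The cost is wording in three sections. The planned five completers, the visits, the tests and the rules for stopping treatment do not change. The one drawback is that the reported cure fraction may be slightly less favourable.

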3.4.2 Study Procedures by Visit

Activities to be performed at each visit are listed below. Please review the *DeviceFarm Device Description* and the *Instructions for Use* documents for details about using the Device and taking photographs with the camera.

CONFIDENTIAL

3.4.2.1 Screening Visit – Baseline

- Obtain Subject's written informed consent prior to initiating any study procedures.
- Document Subject's Informed Consent in the Subject's medical record.
- Screen potential Subject according to the study inclusion/exclusion criteria.
- Take the Subject's medical history.
- Perform a brief physical exam.
- Perform urine pregnancy test on women of childbearing potential.
- Photograph the infected hallux nail(s).
 - If both hallux nails are infected and meet the inclusion/exclusion criteria, both nails can be photographed and tested for KOH and mycology. If both are positive for KOH and culture, the Investigator will choose one and only treat that one in the study.
- Perform KOH testing of infected hallux nail(s): Before obtaining a specimen, make sure the nail is clipped and cleansed with an alcohol swab to remove bacteria and debris.
- Collect mycology sample for lab culture: Prepare and ship the mycology samples according to the instructions from the designated mycology laboratory.

3.4.2.2 Study Visit 1 - Day 1

- Check for conformance to inclusion/exclusion criteria.
- Perform debridement on the infected nail to be treated.
- Notch the nail.
- Measure distance between proximal nail fold and notch.
- Insert the Disposable into the RenewalNail™ plasma treatment device.
- Brush the top, edges, and underside of the infected nail with the Nail Penetration Enhancer.
- Insert the Subject's foot into the opening of the Disposable that was placed the device.
- Ensure that the Subject's foot is properly inserted into the device with a seal of the Disposable flexible material around the foot.
- Push the device power button to start the treatment.
- Complete the 45-minute plasma treatment.
- Perform clinical evaluation of the toes after plasma treatment as specified in “5.0 Safety Assessment/Risks”
- Check on occurrence of adverse events. Stop protocol if any serious adverse events occur.
- Photograph the treated nail.

3.4.2.3 Study Visit 2

Study Visit 2 should occur no sooner than 36 hours after Study Visit 1. In no circumstance should the Subject receive treatment on two (2) consecutive days.

- Check on occurrence of adverse events.
- Perform a plasma treatment per instructions in the *Instructions for Use of the DeviceFarm RenewalNail Plasma Generator DFPD-003* document.
- Perform clinical evaluation of the toes after plasma treatment as specified in “5.0 Safety Assessment/Risks”
- Photograph the treated nail.

3.4.2.4 Study Visit 3

Study Visit 3 should occur no sooner than 36 hours after Study Visit 2, but within 7 calendar days from Study Visit 1. In no circumstance should the subject receive treatment on two (2) consecutive days

- Check on occurrence of adverse events.
- Perform a plasma treatment per instructions in the *Instructions for Use of the DeviceFarm RenewalNail Plasma Generator DFPD-003* document.
- Perform clinical evaluation of the toes after plasma treatment as specified in “5.0 Safety Assessment/Risks”
- Perform fungal scrapings for mycological culture as instructed by the laboratory.
- Photograph the treated nail.

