1.0 INTRODUCTION

Background and Rationale: Onychomycosis, the most common nail disease, accounts for 30% of all cutaneous fungal infections. The disease is a progressive chronic recurring fungal infection affecting an estimated 35 million people in the United States. Approximately 50% of elderly over the age of 70 are infected as well as 30% of diabetics. Although dermatophyte infections are rarely life threatening, their high incidence and prevalence makes them an important health problem. Onychomycosis is not just a cosmetic problem, but can cause pain, difficulty walking, and susceptibility to secondary infections such as cellulitis and osteomyelitis.

Distal subungual onychomycosis (DSO) is the most common form of onychomycosis. DSO is characterized by nail discoloration, onycholysis, dystrophy of the nail plate, and accumulation of subungual debris. There is an average of 4.4 to 5.3 involved toes per patient, with an average of about 2.4 per foot. Approximately 75% of patients have both feet involved.

There are currently three groups of FDA-approved approaches to the treatment of onychomycosis: oral treatments, topical therapy, and laser treatments. Oral terbinafine (Lamisil®, Novartis Pharmaceuticals) is the lead therapy among oral medications consisting of a 250-mg tablet per day for 12 weeks for the treatment of toenail onychomycosis. Oral terbinafine yields the highest complete cure rates, between 38 and 76% depending on the clinical trial design. Oral therapy might be adequate if not for the relatively high risk of liver toxicity and drug-drug interactions. Many patients and their physicians choose not to select oral therapy due to the associated risk. Rare cases of liver failure and serious skin reactions have been reported with oral terbinafine use (Lamisil® package insert).

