3.3.1 Inclusion Criteria

- Subjects who are between 21 to 75 years (inclusive) of age;
- Subjects who are in good general health and free from any clinically significant disease that might interfere with the study evaluations;
- Subjects with established clinical diagnosis of distal subungual onychomycosis;
- Subjects with at least one big toe nail involved with 20-75% infection;
- Subjects with both positive KOH and culture for onychomycosis dermatophytes in screening of nail samples;
- Subjects whose infection is confirmed to be caused by *T. rubrum* or *T. mentagrophytes*;
- Subjects who are willing and able to refrain from employing other (non-study) treatments (traditional or alternative) for his or her toenail onychomycosis throughout study participation;
- Subjects who are willing and able to refrain from the use of nail cosmetics such as clear and/or colored nail lacquers during the week of treatment (from Study Visits 1 through 3);
- Subjects who are willing and able to give written informed consent and able to adhere to procedures and visit schedules;
- Women of childbearing potential who are currently sexually active must agree to use a medically accepted method of contraception while receiving protocol specified treatment. Methods include condoms (male or female), diaphragm or cervical cap with spermicide, medically prescribed intrauterine device, oral or systemic hormonal contraceptive, surgical sterilization (e.g., hysterectomy or tubal ligation);
- Women of childbearing potential who are not currently sexually active must agree to use a

CONFIDENTIAL

medically accepted method of contraception should they become sexually active while participating in the study;

- Women of childbearing potential must have a negative pregnancy test prior to start of study.

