3.3.2 Exclusion Criteria

- Subjects with onychomycosis infection involving lunula of the affected toenail(s) or spikes of disease extending to nail matrix in the affected big toenail;
- Subjects whose foot is too large (larger than US men's size 13) or too small (smaller than US women's size 3) to properly fit into the plasma treatment device;
- Subjects whose affected big toenail cannot become normal in the opinion of the investigator;
- Subjects who received topical antifungal treatment of the nails within 2 weeks before study initiation;
- Subjects who received systemic antifungal treatment within 3 months before study initiation;
- Simultaneous participation in another clinical study or participation in another clinical study in the 30 days directly preceding treatment;
- Subjects who are immunocompromised (e.g. adrenal insufficiency, diabetes mellitus, febrile neutropenia, and the human immunodeficiency virus infected);
- Subjects with any pacemakers, or any metallic implants or prostheses in the vicinity of the treatment site (such as ankle, foot, etc.);
- Subjects with any clinically significant condition or situation, other than the condition being studied that, in the opinion of the investigator, would interfere with study evaluations or optimal participation in the study;
- Subjects who feel they cannot sit for 45 minutes at a time during the treatment;
- Subjects who are part of the staff personnel directly involved with this study or who are family members of the investigational study staff;
- Subjects with known allergy to any of the tested treatment products [i.e. perfluorocarbons and plastic polycarbonate];
- Women who are pregnant, breastfeeding, or planning pregnancy prior to the end of study participation;

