3.4 Conduct of Study

3.4.1 Study Overview by Visit

3.4.1.1 Screening Visit

Subjects are to be screened at the Investigator's facility to determine eligibility for the study. Written informed consent is to be obtained after a careful description of the study. Written, witnessed, informed consent will be obtained from each Subject prior to participation in the study. The Subject will be given adequate time to review the informed consent document as well as address questions and concerns.

Once written informed consent is granted, Screening Visit activities will be carried out as specified in 3.4.2.1. Namely, a medical history is taken and a brief physical examination is conducted. If the Subject is confirmed to meet the inclusion/exclusion criteria besides positive mycological testing, they are assigned a Subject number and results are recorded on the Case Report Form (CRF) for each Subject. Nail scrapings are collected for fungal infection testing by KOH assay and mycological culture. Culture results will be obtained within 4 weeks of Subject's initial screening visit.

A screen failure is a Subject who received information about the study, including signing an informed consent, and possibly performing some study related procedures but was not enrolled, and did not receive study treatment. Only the Subject number, date of visit, date of consent, reason for screen failure, and study status (screen failure) will be captured in the CRF for every screen failure Subject.

3.4.1.2 Study Visit 1

The Subject will be scheduled for the first treatment as soon as positive mycological testing results are available and the Subject is confirmed to meet all inclusion/exclusion criteria. A Subject meeting all of the entry criteria is enrolled into the study. Day 1 activities will be carried out as specified in 3.4.2.2.

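### When both big toenails qualify, Protocol 3.4.2.1 lets the investigator choose the study nail with no criterion fixed in advance, so the more favourable nail can be selected

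*Protocol*

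**What the plan says.** Protocol 3.3.1 sets eligibility by nail: "Subjects with at least one big toe nail involved with 20-75% infection". Both big toenails of one subject can therefore qualify. For that case 3.4.2.1 says that "both nails can be photographed and tested for KOH and mycology", and then: "If both are positive for KOH and culture, the Investigator will choose one and only treat that one in the study".

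The choice depends on both cultures, so it comes after screening. Section 3.4.1.1 states: "Culture results will be obtained within 4 weeks of Subject's initial screening visit". The first treatment is scheduled once positive results are in (3.4.1.2).

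Section 3.2 describes the design as a "Single-center, open-label, pilot study involving 5 Subjects", and Section 2.0 adds: "There will be no placebo arm in the study". Section 9.0 plans subject listings without inference, and says the results will be used to judge whether the treatment is able to produce mycological cure in eligible subjects.

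**The concern.** Two qualifying nails can lie far apart within 20-75% involvement. The investigator decides between them knowing the visible extent of each, and nothing ties the decision to a rule set beforehand. The same investigator takes the endpoint specimen (4.2) and records the growth measurements (4.3).

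With no concurrent control, the listed results will tend to be read against the background cure rates in Section 1.0. Selecting the better nail would move only the study's side of that comparison, and each subject is 1/5 = 20 percentage points. It would also shift the treated nails towards the mild end of the eligible range, so the results would describe a narrower set of nails than the criteria suggest.

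An analysis plan cannot repair this, because the nail is fixed once it has been treated.

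**Working it through.** **Step 1: is the choice limited anywhere?**

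- 3.4.2.1 names the investigator as the one who chooses and gives no criterion.
- 3.3.1 and 3.3.2 limit which nails may enter: the involvement range, no lunula or matrix disease, and an exclusion for "Subjects whose affected big toenail cannot become normal in the opinion of the investigator". These apply before the choice and do not rank two nails that both pass.
- 3.1 has disease severity documented at screening, and 4.1 has baseline photographs of infected nails. Neither requires percent involvement for each nail or a reason for the choice.

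No section limits the choice.

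**Step 2: what can separate the two nails?** The choice arises only when both are positive on KOH and on culture, so those results hardly distinguish them. What remains is clinical extent and appearance.

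**Step 3: how large could the effect be?** The protocol gives no assumed cure rate, sample-size derivation or share of subjects with two qualifying nails, so there is no figure to reproduce. The following is an illustration, and every input except n = 5 is an assumption.

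- Average cure rate of a qualifying nail: p = 10%, 20% or 40%.
- Share of subjects with two qualifying nails: b = 25%, 50% or 75%.
- Each nail has a visible prognostic score s (standard normal), with correlation 0.5 between a subject's two nails.
- The score explains a share R² = 0, 0.1, 0.3 or 0.5 of the latent tendency to cure.

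The cure chance given the score is Φ((t + √R² · s)/√(1 − R²)), with t = Φ⁻¹(p). If the better-looking nail is always picked, s is the larger of the two scores. The average over 400,000 simulated pairs is called p_c. The expected number of cures is 5 × [b · p_c + (1 − b) · p].

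| p | R² | p_c | b = 25% | b = 50% | b = 75% |
|---|---|---|---|---|---|
| any | 0 | p | 5p | 5p | 5p |
| 10% | 0.1 | 12.2% | 0.53 | 0.56 | 0.58 |
| 10% | 0.5 | 14.9% | 0.56 | 0.62 | 0.68 |
| 20% | 0.1 | 23.5% | 1.04 | 1.09 | 1.13 |
| 20% | 0.3 | 26.2% | 1.08 | 1.15 | 1.23 |
| 20% | 0.5 | 28.0% | 1.10 | 1.20 | 1.30 |
| 40% | 0.1 | 44.9% | 2.06 | 2.12 | 2.18 |
| 40% | 0.5 | 51.1% | 2.14 | 2.28 | 2.42 |

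Two entries by hand:

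- p = 20%, b = 25%, R² = 0.1: 5 × (0.25 × 0.235 + 0.75 × 0.20) = 1.04, a gain of 0.04.
- p = 40%, b = 75%, R² = 0.5: 5 × (0.75 × 0.511 + 0.25 × 0.40) = 2.42, a gain of 0.42.

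With p at 20% or 40% and R² above zero, the gain is 0.04 to 0.42 of a cure. With p at 10% it is 0.03 to 0.18. It is zero when visible extent does not predict cure, or when the choice is unrelated to prognosis.

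**The case against.** The strongest reply is that the plan estimates and tests no cure rate. Section 9.0 offers listings from five subjects in an early feasibility study and asks whether cure can be achieved at all. Any nail chosen meets every criterion, so a cure in it still answers that question. The primary endpoint is read by an accredited laboratory (4.2), not by the investigator. This stands as a limit on importance: no error rate is affected, and the issue is how the listed outcomes will be read. It does not defend leaving the choice open, since a rule costs almost nothing and prognosis judgements already have their place in the exclusion criteria.

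Stronger readings that the documents do not support:

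- A reader might infer that the choice will arise often, because Section 1.0 says "Approximately 75% of patients have both feet involved". That figure covers both feet and any toe. Here both big toenails must be 20-75% involved, pass the exclusions and be positive on both tests. Testing the second nail is also only permitted.
- A reader might infer that the KOH and culture results steer the choice. Both nails are positive by definition, so they offer little to choose on.
- A reader might infer that selection would be invisible. Recorded severity and baseline photographs leave it partly visible.
- A reader might state the upward shift as a fact of known size. The protocol gives no data on how involvement relates to culture results soon after treatment. It also does not say that the investigator will prefer the milder nail.

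**Conclusion.** The point holds in a limited form. The protocol leaves the choice between two qualifying nails open, after their extent is known, in an uncontrolled open-label series of five. That permits favourable selection, and where it occurs and extent predicts outcome, the shift is upward. The documents do not show that it will occur, how many subjects it would touch, or how large it would be. The illustration puts it at about 0.04 to 0.4 expected cures in 5 for an average cure rate of 20% or 40%. That rests on the assumed between-nail correlation, predictive strength and bilateral share, and on the better-looking nail always being picked. This is a worthwhile, inexpensive improvement to the design; it does not invalidate the study.

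**What to change.** In 3.4.2.1, replace the investigator's choice with a rule applied before sampling:

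- If both big toenails meet the clinical criteria at screening, designate the study nail before KOH and culture samples are taken. Use a rule unrelated to prognosis, for example right for odd and left for even Subject numbers.
- Use the other nail only if the designated one fails KOH or culture.
- Record and list the percent involvement of both nails.

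The timing matters. Because testing both nails is optional, a rule that starts only after both are found positive could be bypassed by sampling one. The order in 3.4.1.1 already suits the change: the Subject number is assigned once the clinical criteria are confirmed, and the scrapings are described after that. Sequential numbers make the side foreseeable, so the clinical eligibility of each nail should be written down before the number is given.

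The cost is a few lines of protocol text, one recorded percentage per nail, and the loss of investigator discretion between two nails that both already qualify.

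The untreated qualifying nail should not be presented as a within-subject reference for clear growth. The protocol provides for debridement, notching and measurement of the treated nail only, so photographs of the other would not be like for like.
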